### *3.4.1.3 Exploratory Efficacy Variables*

Exploratory efficacy endpoints include the following:

- Change from Baseline (gain or loss) over time in BCVA using the ETDRS.
- Change from Baseline over time in macular volume and CMT as assessed by SD-OCT.
- Proportion of participants with a  $\geq$  2-step or  $\geq$  3-step worsening of DRSS score from Baseline over time.

- BCVA, using the ETDRS, AUC between Baseline and Week 24.
- PK, pharmacogenomic, and flow cytometry/CBC evaluations of interest.
- Change in area of ischemia or area of neovascularization (if PDR develops) from Baseline over time using OCT-A and/or FA (if available at the site).
- Change from Baseline over time in VF as evaluated by perimetry/microperimetry (if available at the site).
- Evaluation of the presence of markers of inflammation [REDACTED] in aqueous humor collected in a single eye in participants who elect to provide these samples.

Best-corrected visual acuity will be assessed using ETDRS charts at 4 meters initial testing distance and assessed in both eyes. The trained technician measuring the BCVA using ETDRS should be the same throughout the study period. Assessments of BCVA will be performed at Visit 1 (Screening), each in-clinic study visit of the Treatment Period, and Visit 9 (EOS). Given the abbreviated scope of the SAP due to the study status, AUC intervals will not be calculated.

Assessments of SD-OCT are described in [Section 3.4.1.2](#). The retinal layers of both eyes will be visualized, and thickness measured by SD-OCT and, if available at the site, additional scans using OCT-A will be obtained. For sites with the capability to perform OCT-A, these assessments should be performed at Visit 2 (Baseline) and Visit 8 (EOT/ET).

The DRSS score as derived from FP and FA findings, is described in [Section 3.4.1.1](#).

Evaluation of VF will be conducted using perimetry and/or microperimetry, per site availability. Evaluations of VF takes approximately 10-20 minutes and will be performed at Visit 2 (Baseline) and Visit 8 (EOT/ET) for sites with the capability to perform the assessment.

Sampling of biomarker, pharmacogenomic, and flow cytometry/CBC will be performed as described Section 17.4 of the clinical study protocol. A PK blood sample will be collected and then centrifuged for collection of plasma samples. Biomarker plasma aliquots will be obtained from the PK samples. Details on aqueous humor collection, plasma biomarkers, blood biomarkers by flow cytometry, and pharmacogenomic evaluation are provided in Section 7.1.1.3.8, 7.2.2.2, 7.2.2.3 and 7.2.2.4 of the clinical study protocol, respectively.

### **3.4.2 Safety Variables**

#### **3.4.2.1 Adverse Events**

An AE is any untoward (unfavorable, harmful, or pathologic) medical occurrence in a participant administered a pharmaceutical (investigational) product even if the event does not necessarily have a causal relationship with this treatment.

An AE can, therefore, be any unfavorable and unintended sign (including an abnormal laboratory finding that is deemed clinically significant), symptom, or disease

temporally associated with the use of a medicinal (investigational) product whether or not related to the medicinal (investigational) product.

All participants who have given informed consent will be evaluated for AEs.

#### *3.4.2.2 Laboratory Parameters*

Blood and urine samples will be collected at each study visit defined in the schedule of events (Section 15 of the clinical study protocol). Laboratory tests will include:

- Hematology: hemoglobin, hematocrit, red blood cell count, white blood cell count with differential, [REDACTED], platelets.
- Chemistry: hemoglobin A1c (HbA1c), glucose, sodium, potassium, calcium, inorganic phosphate, chloride, bicarbonate, magnesium, creatinine, aspartate aminotransferase (AST), alanine aminotransferase (ALT), alkaline phosphatase, lactate dehydrogenase, direct and indirect bilirubin, blood urea nitrogen (BUN), total protein, albumin, and eGFR.
- Serology: hepatitis B virus (HBV), hepatitis C virus (HCV), and human immunodeficiency virus (HIV).
- Coagulation: partial thromboplastin time (PTT), prothrombin time (PT).
- Urinalysis: pH, glucose, erythrocytes, leukocytes, protein, nitrites, UACR.
- Pregnancy: pregnancy testing will be performed at the site in either urine or serum; a positive test result must be confirmed by a serum pregnancy test performed by the central laboratory.

Additional laboratory parameters may be reported. Clinical evaluation of liver injury, including additional testing, may be performed as defined in Section 17.1 of the clinical study protocol. Samples may be used for re-testing, further evaluation of an AE and/or assessment, and follow-up of other exploratory endpoints.

#### *3.4.2.3 Vital Signs*

Vital sign measurements will include seated systolic and diastolic blood pressure (mmHg), heart rate (beats per minute), respiration rate (breaths per minute), and body temperature. Vital signs will be measured after the participant has been seated for 5 minutes. Vital signs will be performed at Screening and every visit in the Treatment Period, Visit 2 (Baseline) through 8 (EOT/ET).

#### *3.4.2.4 12-lead Electrocardiogram*

Twelve-lead electrocardiograms (ECGs) (I, II, III, aVR, aVL, aVF, V1 - V6) will be recorded using a computerized electrocardiograph. A 12-lead ECG will be performed after the participant has rested quietly for at least 5 minutes in a supine position at Visit 1 (Screening), Visit 8 (EOT/ET), and Visit 9 (EOS). In some cases, it may be appropriate to repeat abnormal ECGs to rule out technical factors contributing to ECG artifacts or abnormality. The final interpretation of the ECGs will be recorded on the

appropriate eCRF. The interpretation of the ECGs will be recorded as normal, abnormal but not clinically significant, or abnormal and clinically significant. Heart rate, QT and QT interval corrected for heart rate using Fridericia's correction formula (QTcF) will also be reported.

#### *3.4.2.5 Physical Examination*

At Visit 1 (Screening), a full physical examination will be performed to assess the following organ systems: skin, ears, nose, and throat (ENT), head, eyes, lungs/chest, heart, abdomen, musculoskeletal, extremities, and lymphatic systems. Height and weight will be measured.

During the study period, a targeted physical examination, including auscultation of the heart, measurement of weight, and review of any previous abnormalities identified during the full physical examination will be performed.

#### *3.4.2.6 Additional Ophthalmological Assessments*

Additional ophthalmological assessments performed include:

- Slit lamp examination (dilated and undilated)
- Extended Ophthalmoscopy
- Intraocular pressure measurements (IOP)
- Gonioscopy

The slit lamp examination, IOP measurement, gonioscopy, and extended ophthalmoscopy are to be performed in both eyes. The anterior and posterior segments of the eye should be assessed. Extended ophthalmoscopy is an assessment of the peripheral retina, usually performed with a 20 diopter lens and an indirect ophthalmoscope, to examine for retinal abnormalities such as retinal tears, detachment, hemorrhage, retinal artery perfusion, etc. Intraocular pressure will be measured using applanation Goldmann tonometry in both eyes during each visit. A gonioscope, together with a slit lamp or operating microscope, will be used to view the iridocorneal angle. Extended ophthalmoscopy is an assessment of the peripheral retina after pupillary dilation, usually performed with a 20 diopter lens and an indirect ophthalmoscope, to examine for retinal abnormalities such as neovascularization, retinal tears, detachment, retinal hemorrhage, etc. Assessments will be performed at each study visit defined in the schedule of events (Section 15 of the clinical study protocol).

#### *3.4.3 Pharmacokinetic Variables*

Plasma concentration measurements of AKST4290 and its major metabolites will be collected to assess systemic exposure. Sampling of PK will be performed as described Section 17.4 of the clinical study protocol.

### **3.5 Data Quality Assurance**

Report summaries will be generated using validated Base SAS® software, version 9.4 or higher, on a PC or server-based platform. Additional validated software may be used to generate analyses, as needed.

All SAS programs that create outputs or supporting analysis datasets will be validated by a second statistical programmer or biostatistician. At a minimum, validation of programs will consist of a review of the program log, review of output or dataset format and structure, and independent confirmatory programming to verify output results or dataset content. Additionally, all outputs will undergo a review by a senior level team member before finalization.

The content of the source data will be reviewed on an ongoing basis by project statistical programmers and statisticians. Data will be checked for missing values, invalid records, and extreme outliers through defensive programming applications, analysis-based edit checks, and other programmatic testing procedures. All findings will be forwarded to the project data manager for appropriate action and resolution.

## 4. STATISTICAL METHODS

### 4.1 General Methodology

Data will be summarized by Emanate biostatistics personnel. Given the paucity of study participants, data collected during the study and follow-up period will be reported with listings, presented in rich text format, and using recommended ICH numbering. Output specifications for all listings will be in conformance with guidelines specified by the ICH in Appendix 7 of the Electronic Common Technical Document Specification (Apr 2003).

#### 4.1.1 *Reporting Conventions*

In general, all data collected and any derived data will be presented in subject data listings for all enrolled subjects. Listings will be ordered by site, subject number, treatment group, and assessment or event date. The treatment group presented in listings will be based upon the actual treatment received.

#### 4.1.2 *Summarization by Visit*

All data, including unscheduled visits, will be included in subject listings.

#### 4.1.3 *Data Handling Rules*

Values reported as greater than or less than some quantifiable limit (eg, “<1.0”) will be presented as collected in the subject listings.

#### 4.1.4 *Standard Calculations*

Where appropriate, the calculated study day of each assessment or event will be presented with the assessment or event date on subject data listings, where study day will be determined as:

- The assessment/event date minus the date of first dose of study drug, if the assessment/event date is prior to the date of first dose; and
- The assessment/event date minus the date of first dose of study drug, plus one, if the assessment/event date is on or after the date of first dose.

Other variables requiring calculations will be derived using the following formulas:

- **Days:** A duration between two dates expressed in days will be calculated using the following conventions:
  - Later date – earlier date + 1, if the earlier date is on or after the date of first dose of study drug; or
  - Later date – earlier date, if the earlier date is prior to the date of first dose of study drug.
- **Years:** A duration expressed in years will be calculated by dividing the duration in days by 365.25.

## 4.2 Study Subjects

### 4.2.1 Disposition of Subjects

Subject disposition will be presented in a listing to include the date of first dose, study exit date, subject status and reason for early termination (when applicable). Whether or not the subject was unmasked including the date/reason when applicable will also be reported. A listing of screen failures, to include the date of study exit and reason for screen failure, will also be presented.

### 4.2.2 Protocol Deviations

Major and minor protocol violations will be presented in a listing. Major protocol violations are protocol deviations captured on-study that are deemed by the Sponsor to potentially impact the efficacy or safety conclusions of the study.

All major protocol violations will be determined and appropriately categorized prior to database lock and prior to breaking the mask of the treatment group assignments.

### 4.2.3 Plasma Concentrations

Raw plasma concentration values for AKST4290 and the corresponding metabolites, M737 and M227, will be provided in listings by sampling time point for participants receiving AKST4290.

### 4.2.4 Pharmacokinetic Analysis

Pharmacokinetic parameters will not be derived due to the limited number of sampling timepoints.

## 4.3 Efficacy Evaluations

Given the abbreviated scope of the SAP due to the study status, efficacy endpoint analysis will be presented in subject data listings, generally relying on the data as collected in the electronic data capture (EDC) system or from the central reading center.

#### ***4.3.1 Demographic and Other Baseline Characteristics***

Demographic variables including age, sex, ethnicity, race and childbearing potential will be presented in a listing. Baseline disease characteristics include diabetes mellitus (DM) type category (Type 1 or Type 2), time since date of DM diagnosis, time since DR diagnosis for oculus dexter (OD) and oculus sinister (OS) eyes, and baseline DRSS levels for OD and OS eyes. Time since DM or DR diagnosis (in years) is calculated as the informed consent date – the date of diagnosis (DM or DR) divided by 365.25.

Medical history will be presented in a listing. Verbatim terms on case report forms will be mapped to preferred terms and system organ classes using the Medical Dictionary for Regulatory Activities (MedDRA, version 24.0).

#### ***4.3.2 Measurements of Treatment Compliance***

Compliance to study treatment regimen will be reported as collected on the Study Drug Administration and Accountability eCRF page. The number of tablets dispensed and returned for each visit will be presented in a listing. A separate listing will be provided to present any administration information reported on the Missed/Additional Doses eCRF page.

#### ***4.3.3 Efficacy Endpoint Analysis***

The DRSS level determined for each eye, OD and OS, will be presented as reported by the central reading center in the fundus photography (Fundus Photography Modified 7 Field [FP-7M] or Fundus Photography 4 Wide [FP-4W]) assessment; a single bilateral severity level will not be derived to determine step-wise improvements/worsening over time. Assessments of FA will also be reported in a listing.

Subjects that progress to any vision-threatening complication that requires treatment (CI-DME, PDR, and/or ANSV) will be reported in a listing to include the vision-threatening complication type, confirmation details associated with the progression, and any corresponding treatment information. Additionally, the treatment of PDR review criteria collected by the center reading center will also be presented in a listing, as applicable.

Effect of AKST4290 on diabetic kidney disease as assessed by eGFR and UACR will be presented in the corresponding laboratory listings as described in [Section 4.4.4](#).

Responses to WPAI-GH questionnaire, as well as the corresponding derived impairment percentages described in [Section 3.4.1.2](#), will be presented in a listing.

Results for assessments of BCVA using ETDRS, SD-OCT, OCT-A (as available at the site), and VF (as available at the site) will be presented in a listing.

Presentation of pharmacogenomics data will generally be conducted by a separate vendor and is outside the scope of this analysis plan. [REDACTED]

[REDACTED]

These biomarkers will be measured in plasma samples to investigate any change in response to treatment. Blood biomarkers using flow cytometry/CBC will be measured to characterize immune cells. Flow cytometry results will be presented in a listing. Additional summary and/or presentation of biomarkers data will be conducted by a separate vendor and are outside the scope of this analysis plan.

#### **4.4 Safety Evaluation**

Safety listings will include all subjects who receive at least one dose of study drug. Subjects who do not complete the study, for whatever reason, will have all available data up until the time of termination included in the analysis.

##### ***4.4.1 Extent of Exposure***

Extent of exposure to study treatment will be provided in listings. The duration of exposure will be presented in days and calculated as the date of last dose of study drug minus the date of first dose of study drug, plus one. Total dose received (mg) will be calculated as the total number of tablets dispensed – total number of tablets returned, multiplied by 400.

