6.1.4. Dosing and Administration

Study drug will be self-administered orally b.i.d., approximately 12 hours apart. AKST4290 will be administered as a TDD of 800 mg (400 mg b.i.d.). Matching placebo will be self-administered orally b.i.d. following the same dosing instructions as AKST4290.

Participants will receive training on study drug administration prior to initial study drug administration at Visit 2. Study drug will be self-administered in the clinic under the supervision of study personnel during every in-clinic visit of the Treatment Period (Visits 2-8) after any pre-dose assessments (including PK sample collection), and then self-administered at home between study visits.

When study drug is dispensed, participants will receive a total of 5 packets, which represents a 5-week supply (4 weeks of treatment plus an additional week). Study drug accountability will be assessed by packet.

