### 3.3 Treatment

### ***3.3.1 Treatment Administered***

Study treatment consists of AKST4290 or matched placebo. AKST4290 is a film-coated pink, oblong tablet manufactured by Alkahest, Inc., with a unit strength of 400 mg and is packaged in “foil-foil” blister packets. Each packet will include 14 tablets.

Study drug will be self-administered orally b.i.d., approximately 12 hours apart. AKST4290 will be administered as a total daily dose of 800 mg (400 mg b.i.d.). Matching placebo will be self-administered orally b.i.d. following the same dosing instructions as AKST4290.

Participants will receive training on study drug administration prior to initial study drug administration at Visit 2. Study drug will be self-administered in the clinic under the supervision of study personnel during every in-clinic visit of the Treatment Period (Visits 2-8) after any pre-dose assessments (including PK sample collection), and then self-administered at home between study visits.

When study drug is dispensed, participants will receive a total of 5 packets, which represents a 5-week supply (4 weeks of treatment plus an additional week). Study drug accountability will be assessed by packet.

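### The SAP's total-dose formula has no arm restriction, so it would list milligrams for a placebo participant, and it counts any unreturned tablet as taken

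*SAP*

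**What the plan says.** SAP 4.4.1 (Extent of Exposure) defines two variables. Duration of exposure is "calculated as the date of last dose of study drug minus the date of first dose of study drug, plus one". Total dose received, in mg, is the number of tablets dispensed minus the "total number of tablets returned, multiplied by 400". Neither definition mentions treatment arm.

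Three other statements set the scope of that formula:

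- SAP 4.4 (Safety Evaluation): "Safety listings will include all subjects who receive at least one dose of study drug".
- SAP 3.3.1 (Treatment Administered): "Study treatment consists of AKST4290 or matched placebo". The phrase "with a unit strength of 400 mg" in that section describes the AKST4290 tablet.
- SAP 4.2.3 (Plasma Concentrations) restricts its listing to AKST4290 recipients, so the SAP does limit by arm where it intends to.

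On supply and counting, SAP 3.3.1 says "Each packet will include 14 tablets", and both documents give five packets per dispensing to cover four weeks plus one spare week. Protocol 6.1.4 says "Study drug accountability will be assessed by packet", whereas SAP 4.3.2 (Measurements of Treatment Compliance) lists tablets dispensed and returned by visit. On dosing irregularities, SAP 4.3.2 adds: "A separate listing will be provided to present any administration information reported on the Missed/Additional Doses eCRF page". The total-dose formula makes no use of that page.

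**The concern.** There are two separate problems, and the first is the firmer.

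1. **Placebo.** A column headed total dose received in mg should be 0 mg of AKST4290 for someone who took placebo tablets. The rule as written multiplies placebo tablets by 400, so a programmer who follows it prints a value that is wrong for that participant.
2. **Unreturned tablets.** The quantity calculated is supply not returned, but it is labelled as dose received. Each dispensing carries a spare week, so there are normally tablets that should come back. The SAP gives no rule for the case where they do not. It also does not say how the result relates to the date-based duration in the same section or to the Missed/Additional Doses listing.

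What is at stake is the accuracy of one derived column. SAP 4.1 and 4.6 reduce all output to listings because only three participants were randomized, so each row is read on its own.

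**Working it through.** **Inputs**

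- Tablets per packet: 14 (SAP 3.3.1).
- Packets per dispensing: 5 (Protocol 6.1.4; SAP 3.3.1).
- Dosing: one tablet twice daily, so 2 tablets per day (same sections).
- Interval between dispensings: 4 weeks = 28 days.
- Factor: 400 mg per tablet (SAP 4.4.1).

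**Step 1. Reproduce the plan's own figure.** 5 × 14 = 70 tablets; 70 / 2 = 35 days = 5 weeks. This matches the stated five-week supply, so the supply arithmetic is sound.

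**Step 2. Planned use in one interval.** 28 × 2 = 56 tablets; 56 × 400 = 22,400 mg. Spare tablets: 70 − 56 = 14, which is one packet, or 14 × 400 = 5,600 mg.

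**Step 3. Placebo participant, fully adherent, all spare tablets returned.** Formula: (70 − 14) × 400 = 22,400 mg. AKST4290 received: 0 mg.

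**Step 4. AKST4290 recipient, 56 tablets taken, some of the 14 spare tablets neither taken nor returned.** With L tablets not returned, the formula gives (70 − (14 − L)) × 400 and the overstatement is 400 × L.

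| L | Formula (mg) | Overstatement (mg) | Relative to 22,400 mg |
|---|---|---|---|
| 0 | 22,400 | 0 | 0% |
| 1 | 22,800 | 400 | 1.8% |
| 7 | 25,200 | 2,800 | 12.5% |
| 14 | 28,000 | 5,600 | 25% |

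In the last row, 28,000 mg over 28 days is 1,000 mg per day, against the planned 800 mg per day. Setting the value beside the date-based duration would therefore reveal the discrepancy.

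**Step 5. Mid-interval stop (illustrative assumption: 14 tablets taken, nothing returned).** Formula: 70 × 400 = 28,000 mg. Taken: 14 × 400 = 5,600 mg. The 25% ceiling in step 4 therefore applies only to a fully dosed interval.

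**Step 6. Order of operations.** The formula has no parentheses. If the multiplication were done first, the step 3 inputs would give 70 − 14 × 400 = −5,530. The comma in the sentence makes the intended order clear enough, but brackets would remove the doubt.

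**The case against.** The strongest case on the other side is that this is a conventional accountability measure and the documents contain safeguards around it.

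- Dispensed minus returned is exact for AKST4290 recipients whenever untaken tablets come back. Protocol 6.2 requires the site to verify at final reconciliation that participants have returned all unused drug, and the Schedule of Events places accountability at the treatment visits. The documents contain no return data, so an error in the active arm is possible but not shown.
- Listings show the treatment actually received (SAP 4.1.1). A placebo mg value would therefore stand next to a placebo label. Tablet counts by visit and missed or additional doses are also listed, so a careful reader could spot and correct the figure.
- No summary, test or exposure-response analysis uses the value.
- The mismatch between packet and tablet counting is one of wording. It does not show that tablet counts are unavailable.

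All of this stands, and it keeps the point small. It does not remove it. A visible label beside a wrong number does not correct the rule that produced it, and the return checks have no bearing on the placebo problem.

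A reader might infer more than the documents support in three ways:

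- **That the exposure listing as a whole is wrong.** It is not: duration comes from dose dates and is untouched.
- **That the error should be scaled to 24 weeks.** A full course is 168 × 2 × 400 = 134,400 mg, and six unreturned spare packets would make it 168,000 mg. But the three participants were on drug when the study was terminated and then had to stop, so none is shown to have completed a full course.
- **That liver findings would be misjudged because of this column.** The study was stopped after liver enzyme findings in other AKST4290 studies, but no section says that liver results will be read against total mg.

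**Conclusion.** The point holds as a minor correction to one listed variable.

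- **Placebo.** As written, the rule gives a wrong value for any placebo participant: 22,400 mg instead of 0 mg of AKST4290 per fully adherent 4-week interval with all spare tablets returned. This follows from the text alone. Whether it affects anyone is unknown, because the arm split of the three randomized participants is not given.
- **AKST4290.** The overstatement runs from 0 to 5,600 mg (25%) per fully dosed 4-week interval, depending on how much of the spare packet is untaken and unreturned. It is larger if a participant stops mid-interval and returns nothing. The upper figures are conditional on incomplete returns, which the documents neither report nor make likely.

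The per-interval figures assume two tablets daily for 28 days from one dispensing of 70 tablets.

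**What to change.** In SAP 4.4.1:

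1. Calculate mg only for participants who received AKST4290. For placebo, list tablet counts or 0 mg.
2. Put parentheses around the subtraction: (tablets dispensed − tablets returned) × 400.
3. Label the value as an accountability-based dose.
4. Flag unreturned tablets as unaccounted for, with a cross-reference to the date-based duration and to the Missed/Additional Doses listing.

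Keep dispensed minus returned as the derivation. The obvious alternative is twice the days of exposure, less missed and plus additional doses. It assumes adherence unless a miss is reported, and it miscounts partial first and last days, so it is not clearly better.

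It would also help to align the packet-based accountability wording in Protocol 6.1.4 and SAP 3.3.1 with the tablet counts used in SAP 4.3.2 and 4.4.1.

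The cost is a few lines of SAP text, one condition in a derivation and a column label or footnote. The tablet counts and missed-dose data are already collected.
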